14.6 Changes to the approved clinical study protocol

Any proposed change to the approved final CSP will be documented in a written and numbered CSP amendment. All substantial amendments to the CSP must be approved by the appropriate IEC and/or CA before implementation according to applicable regulations.

14.7 Audits and inspections

Authorised representatives of Sponsor, a CA, or the IEC may perform audits or inspections at the study site, with permission from the Investigator to have direct access to source data/documents. The purpose of an audit or inspection is to systematically and independently examine all study-related activities and documents, to determine whether these activities were conducted, and data were recorded, analysed, and accurately reported according to the CSP, ICH-GCP guidelines, GDPR and any applicable regulatory requirements. The Investigator will contact the Sponsor immediately if contacted by a CA about an inspection at the study site.

14.8 Insurance

Subjects will be covered under a liability insurance policy through the Swedish Pharmaceutical Insurance (Läkemedelsförsäkringen). The certificate of insurance and an information leaflet containing essential information about the insurance coverage can be provided upon request. The participating subjects are also protected in accordance with national regulations, as applicable. CTC has a company insurance covering services performed by CTC.

15 STUDY MANAGEMENT

15.1 Training of study site personnel

Before enrolment of the first subject, a Sponsor representative or delegate will perform a study initiation visit at the study site. The requirements of the CSP and related documents will be reviewed and discussed, and the investigational staff will be trained in any study-specific procedures and systems utilised.

It is the responsibility of the Principal Investigator to ensure that all personnel involved in the study are fully informed of all relevant aspects of the study and have a detailed knowledge of and training in the procedures that are to be executed by them. Any new information of relevance to the performance of this study must be forwarded to the staff involved in a timely manner.

The Investigator will keep a list of all personnel involved in the study together with their function and study-related duties delegated. A Curriculum Vitae will be available for all staff to whom study-specific duties are delegated.

15.2 Clinical monitoring

The Sponsor is responsible for securing agreement from all involved parties to ensure direct access to all study-related sites, source data/documents, and reports for the purpose of monitoring and auditing by the Sponsor, and inspection by domestic and foreign CAs.

As defined in the risk-based monitoring (RBM) plan, approved by the Sponsor and provided separately, the responsible Monitor will periodically visit the study site at times agreed upon by the Investigator and the Monitor. Adaptations related to the on-site monitoring plan, when it is impossible or inappropriate to follow due to the COVID-19 pandemic, may be required such as supplementation with (additional/increased) centralised monitoring and central review of data if considered possible and meaningful (see Table 6.6-1). Results of adjusted monitoring/review measures should be reported to the Sponsor in monitoring reports and in the CSR. At the time of each monitoring visit, the role of the Monitor is (but not limited to) to:

- provide information and support to the investigational team
- confirm that facilities and resources remain acceptable
- confirm that the investigational team is adhering to the CSP, applicable SOPs, guidelines, manuals, and regulatory requirements
- verify that data are being accurately and timely recorded in the eCRFs and that IMP accountability checks are being performed
- verify that data in the eCRF are consistent with the clinical records (SDV) in accordance with the RBM plan
- verify that the correct informed consent procedure has been adhered to for participating subjects
- ensure that withdrawal of informed consent to the use of the subject's biological samples will be reported and biological samples are identified and disposed of/destructed accordingly, and that this action is documented and reported to the subject

- verify that AEs are recorded and reported in a timely manner and according to the CSP
- raise and escalate any serious quality issues, serious GCP breach and any data privacy breach to the Sponsor

Centralised monitoring will also be performed continuously by study team members at CTC in accordance with the RBM plan.

When the study has been completed and all queries have been resolved and the database has been locked, the Monitor will perform a close-out visit.

15.3 Source data documents

A separate *Origin of Source Data List* will be generated for the study site before start of enrolment, specifying the location of the source of derived information appearing in the eCRF. This document must be signed by the Principal Investigator and the Monitor to confirm agreement before start of recruitment.

Source documents are all documents used by the Investigator or hospital that relate to the subject's medical history, that verifies the existence of the subject, the inclusion and exclusion criteria, and all records covering the subject's participation in the study. They include laboratory notes, memoranda, material dispensing records, subject files, etc. The eCRF may constitute source data if clearly defined in the *Origin of Source Data List*.

The Investigator should guarantee access to source documents to the Monitor, CAs and the IECs, if required.

15.4 Study agreements

The Principal Investigator must comply with all the terms, conditions, and obligations of the *Clinical Study Agreement* for this study.

Agreements between Sponsor and CTC must be in place before any study-related procedures can take place, or subjects be enrolled.

15.5 Study timetable and end of study

The study is expected to be performed in Q1 2022.

A subject is considered to have completed the study if he has completed all study visits and contacts including the end-of-study phone call.

The end of the clinical part of the study is defined as the end-of-study phone call of the last subject participating in the study.

15.6 Termination of the study

The Investigator or the Sponsor may terminate this study prematurely for any reasonable cause. The IEC and CA should be informed promptly. Conditions that may warrant study termination include, but are not limited to:

- The discovery of an unexpected, significant, or unacceptable risk to the subjects enrolled in the study or potential study subjects; or
- A decision by the Sponsor to suspend or discontinue development of the IMP

If the CA obtains information that raises doubts about the safety or scientific validity of the clinical study, the CA can suspend or prohibit the study. Before the CA reaches its decision, it shall, except where there is imminent risk, ask the Sponsor and/or the Investigator for their opinion, to be delivered within 1 week (Directive 2001/20/EC, Article 12, Section 1).

If the study is prematurely terminated or suspended for any reason, the Investigator/institution should promptly inform the subjects and should assure appropriate follow-up for the subjects.

15.7 Reporting and publication

15.7.1 Clinical Study Report

A summarising report must be submitted to the applicable CA and IEC within 12 months after completion of the study (in accordance with LVFS 2011:19, Chapter 9).

A CSR, in compliance with ICH-E3, describing the conduct of the study, any statistical analyses performed, and the results obtained, will be prepared by CTC. The report will be reviewed and approved by, as a minimum, the Principal Investigator, the Statistician, and the Sponsor. The study results will be reported in the EudraCT database per applicable regulations within 12 months after completion of the study.

15.7.2 Annual safety report

If the study duration exceeds 1 year, the Sponsor must submit a development safety update report (DSUR) to the CA and to the IEC. The report shall summarise all pertinent safety information collected during the reporting period and contain an update of the risk-benefit evaluation if there has been any change since the approval of the clinical study.

15.7.3 Confidentiality and ownership of study data

Any confidential information relating to the IMP or the study, including any data and results from the study, will be the exclusive property of the Sponsor. The Investigator and any other persons involved in the study are responsible for protecting the confidentiality of this proprietary information belonging to the Sponsor.

15.7.4 Publication

The results from this study may be submitted for publication at the discretion of the Sponsor.

15.8 Archiving

Records and documents pertaining to the conduct of this study should be retained by the investigator for 25 years after study completion unless local regulations or institutional policies require a longer retention period. This includes any original source documents related to the study, the *Subject Identification List* (providing the sole link between named subject source records and pseudonymous eCRF data), the original signed ICFs and detailed records of disposition of IMP. It is the responsibility of the Sponsor to inform the Investigator/institution as to when these documents no longer need to be retained.

The Sponsor will archive the TMF in accordance with ICH E6 GCP, Section 8 and applicable regulatory requirements.

The data from the eCRFs (including metadata, audit trail and closed queries) will be sent to the Sponsor and a copy will be retained at the clinic and filed in the ISF for archiving for 25 years after finalisation of the CSR.

The completed eCRFs are the property of the Sponsor and should not be made available in any form to third parties, except for authorised representatives of appropriate Health/Regulatory Authorities, without written permission from the Sponsor.

16 DATA MANAGEMENT

The data management routines include procedures for handling of the eCRF, database set-up and management, data entry and verification, data validation, QC of the database, and documentation of the performed activities including information of discrepancies in the process. The database, data entry screens, and program will be designed in accordance with the CSP.

Data validation/data cleaning procedures are designed to assure validity and integrity of the clinical data. These procedures consist of computerised online edit checks identifying *e.g.* data values that are outside the allowed range and SAS-programmed batch checks and data listing for data quality reviews on data exports. All study-specific and standard data validation programming will be tested in a separate testing environment prior to use on production data.

Detailed information on data management processes will be described in a study-specific *Data Management Plan*.

16.1 The web-based eCRF

Clinical data will be entered into a 21 CFR Part 11-compliant eCRF (Viedoc[™]) provided by Viedoc Technologies AB. The eCRF includes password protection and internal quality checks, such as automatic range checks, to identify data that appear inconsistent, incomplete, or inaccurate. Clinical data will be entered directly from the source documents or at bedside (if the eCRF data constitutes source data). Source data are to be defined at the study site before inclusion of the first subject (Section 15.3).

Authorised site personnel designated by the Investigator will complete data collection. Appropriate eCRF training and security measures for access control will be completed with the Investigator and all authorised site personnel prior to the study being initiated and any data being entered into the system for any study subject.

16.2 The entering of data into the eCRF

All entries, corrections, and alterations are to be made by the Investigator or designee. Neither the Monitor nor any other study team member besides site staff can enter data in the eCRF. All data should be entered in English.

The eCRFs should be completed as soon as possible during or after the subject's visit. To avoid inter-observer variability, every effort should be made to ensure that preferably the same individual who made the initial baseline determinations completes all corresponding follow-up evaluations.

The Investigator must verify that all data entries in the eCRFs are accurate and correct. If some assessments are not done, or if certain information is not available, not applicable, or unknown, the Investigator or assigned clinical staff should record such information in the eCRF. The Investigator will be required to electronically sign off the clinical data. This will be performed by means of the Investigator's unique User ID and password; date and time stamps will be added automatically at time of electronic signature.

16.3 The query process

The Monitor will review the eCRFs and evaluate them for completeness and consistency, according to the RBM plan. Data in the eCRF will be compared with the respective source documents to ensure that there are no discrepancies for critical data as described in the RBM plan. All entries, corrections, and alterations are to be made by the Investigator or designee. Neither the Monitor nor any other study team member besides site staff can enter data in the eCRF.

If corrections are needed, queries will be raised within the eCRF, either because of built-in edit checks or manually raised by the Monitor. An appropriate member of the site staff will answer the queries in the eCRF either by correcting the data or by entering a response to the query. The Monitor will either approve the answer/correction or re-issue the query.

16.4 Audit trail

All entries in the eCRF will be fully recorded in a protected, readable, and not editable audit trail. Once clinical data have been saved, corrections to the data fields will be audit trailed, meaning that the reason for change, the name of the person who made the change, together with time and date will be logged.

16.5 External data

External data consists of data that are not recorded in the eCRF (*i.e.* safety laboratory data and FBF data). Data may be received in electronic format or as a paper printout. Key variables are defined to uniquely identify each sample record. File and data formats are agreed with the external data provider.

Reconciliation of external data versus eCRF data will be performed ensuring data integrity.

16.6 Medical coding

Medical coding will be performed by trained personnel at CTC. Medical/surgical history verbatim terms and AEs will be coded using the Medical Dictionary of Regulatory Activities (MedDRA; latest version available at start of eCRF set up). Prior and concomitant medications will be coded according to the World Health Organisation (WHO) anatomic therapeutic chemical (ATC) classification system. All coding will be approved by Sponsor prior to database lock.

16.7 Database lock

When all data have been entered, discrepancies resolved, SDV has been performed according to the RBM plan, all external data and SAEs have been successfully reconciled, all medical terms have been coded, all protocol deviations have been categorised, and all Principal Investigator signatures have been collected, clean file will be declared after the classification of the subjects to the analysis populations, the database will be locked, and the data will be ready for analysis.

17 STATISTICAL METHODS AND DETERMINATION OF SAMPLE SIZE

The principal features of the statistical analysis to be performed are described in this section. A more technical and detailed elaboration of the principal features will be presented in a separate *Statistical Analysis Plan*, which will be signed and approved prior to database lock.

Analyses of the primary and secondary endpoints will be performed by CTC.

17.1 General

Continuous data will be presented in terms of evaluable and missing observations, arithmetic mean, standard deviation (SD), median, minimum, and maximum value. Categorical data will be presented as counts and percentages. When applicable, summary data will be presented by treatment (test product/comparator), and by assessment time. Individual subject data will be listed by subject number, treatment, and, where applicable, by assessment time.

All descriptive summaries and statistical analyses will be performed using SAS Version 9.4 or later (SAS Institute, Inc., Cary, NC).

Baseline for the safety assessments will be defined as the last data collection point prior to the first administration of IMP. For the FBF measurements, a baseline will be defined for each dose level.

No imputation of missing data will be performed.

17.2 Determination of sample size

No formal sample size calculation has been performed for this study. The proposed sample size is considered sufficient to provide adequate information for the study objectives.

Approximately 10 subjects will be screened to achieve 5 included and evaluable subjects.

17.3 Analysis data sets

17.3.1 Full analysis set

The full analysis set (FAS) will consist of all subjects who have been included and received at least one dose of IMP and have at least one post-baseline assessment.

17.3.2 Safety analysis set

The safety analysis set will compromise all subject who received at least one dose of the IMP.

17.4 Description of study population

17.4.1 Demographics and baseline characteristics

Descriptive statistics for demographics, weight, height, BMI, and dominant/non-dominant arm will be presented.

Individual data will be listed by subject.

17.4.2 Medical/surgical history and prior/concomitant medication

Medical/surgical history will be summarised by system organ class (SOC) and preferred term (PT). Prior/concomitant medications will be presented by ATC level 4 and 5.

Individual data will be listed by subject.

17.4.3 Physical examination

Clinically significant and non-clinically significant abnormal findings will be specified and presented by subject.

Individual data will be listed by subject.

17.4.4 Treatment compliance

The number of subjects administered each IMP and start and stop times for each infusion will be listed.

17.5 Analysis of efficacy endpoints

17.5.1 Effect of C21 on forearm blood flow

The response to increasing i.a. doses of C21 will be summarised using descriptive statistics with percent change from baseline and presented by dose.

17.5.2 Dose-response

The dose response curve of C21 will be presented using a mixed model. The natural logarithm of the maximum FBF value for each dose level and each subject will be used as the dependent variable in the model. Dose will be used as a class variable and subject as a random variable. Kenward-Roger's approximation for degrees of freedom will be used. The least square means (LSMeans) estimates for the doses will be presented in a plot. In addition, the pairwise LSMeans differences between the doses will be tabulated.

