7.1.1 Primary endpoint

The primary endpoint is percent change from baseline in FBF, in response to increasing i.a. doses of C21.

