9.9 Randomisation and blinding

Randomisation will not be used. This is an open-label study and all subjects will receive the same IMP and undergo the same study procedures.

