11.2 Efficacy assessments

11.2.1 Strain-gauge venous occlusion plethysmography

Measurements of FBF will be performed using a CE-marked automated strain-gauge venous occlusion plethysmography equipment providing on-line measurements; Bergenheim, Elektromedicin, Göteborg, Sweden.

The underlying principle of this method is that when the venous return from the forearm is briefly interrupted by inflating a cuff placed around the upper arm to well above venous pressure but below diastolic pressure, and arterial inflow continues unimpeded, the forearm swells at a rate proportional to the rate of arterial inflow. Changes in forearm volume result in a corresponding change in arm circumference and thus strain-gauge length, which can be detected as an alteration in electrical resistance of the gauge, and thus potential difference [16].

The subject will be placed resting in a comfortable supine position in a quiet room with normal room temperature (+20 °C to +25 °C) [14]. Both forearms must be positioned above the level of the heart to ensure adequate venous emptying during the period of deflation. This position will be achieved by resting the elbows on foam pads and supporting the hands with pillows. Cuffs will be placed on the widest part of both forearms and a smaller cuff will be placed around each wrist. The non-infused arm is used as a contemporaneous control to account for any minor changes in FBF affecting both arms, *e.g.* emotional stress or temperature changes.

A catheter will be inserted into the brachial artery of the nondominant arm according to standard hospital procedures. A standard arterial cannula will be used. The artery will be palpated at the elbow of the non-dominant arm. The skin will be cleaned with alcohol after which the artery is cannulated transcutaneously. A small infusion of saline will be connected to maintain the line opened.

After cannulation there will be a resting period of approximately 25 min. At the end of this resting period, baseline measurements of FBF will be performed.

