The subject will receive ascending doses of C21 (3, 10, 30, 100 and 200 μ g/min) through local i.a. infusions for 5 min/dose with an infusion rate of 1 mL/min or 2 mL/min for the 200 μ g/min dose. The start -and stop times of the infusions will be recorded. Measurements of FBF will be performed in both arms simultaneously during the last 2 min of each infusion. The C21 doses will be separated by a wash-out period of at least 15 min. At the end of each wash-out period FBF will be measured and a baseline value for the next dose be recorded.

For each FBF measurement, an inflation pressure of 60 mmHg will be used for intervals of approximately 7 sec followed by approximately 8 sec of deflation. This cycle will be repeated approximately 8 times during the last 2 min of each infusion. The wrist cuff will be inflated to supra-systolic pressures within 30 sec before each measurement to exclude the hand circulation. Changes in forearm volume will be measured using strain-gauges placed around the widest part of the forearms. A measure of blood flow to that part of the forearm enclosed by the two cuffs is provided, expressed as mL per 100 mL of forearm volume per minute. Actual forearm volume can be estimated by calculation, assuming the forearm is a simple truncated cone, or by simple water displacement.

When the last C21 dose has been administered, the infusion will be discontinued and there will be a resting period of 20 min. At the end of this resting period, FBF will be measured and a baseline value for the first sodium nitroprusside dose will be recorded.

Infusions of sodium nitroprusside solution (Nipruss[®]) will be performed as a positive control, using the same methodology as described above. Ascending doses of 0.8, 1.6, and 3.2 μ g/min will be administered.

After removal of the arterial catheter a compression bandage will be applied to prevent bleeding.

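### The dose-response model leaves out the per-dose baseline, so with one fixed ascending order its curve cannot separate dose from drift over the session

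*Combined protocol and SAP*

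**What the plan says.** The primary endpoint is baseline-referenced (Section 7.1.1: "The primary endpoint is percent change from baseline in FBF, in response to increasing i.a. doses of C21"). Section 17.1 supports it: "For the FBF measurements, a baseline will be defined for each dose level". Section 11.2.1 collects the data: "At the end of each wash-out period FBF will be measured and a baseline value for the next dose be recorded". The primary analysis in Section 17.5.1 is descriptive: "The response to increasing i.a. doses of C21 will be summarised using descriptive statistics with percent change from baseline and presented by dose".

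The dose-response curve is a separate secondary endpoint. Section 17.5.2, repeated in the synopsis, sets the response: "The natural logarithm of the maximum FBF value for each dose level and each subject will be used as the dependent variable". The only model terms are dose (class) and subject (random), with Kenward-Roger degrees of freedom. The outputs are a plot of the dose LSMeans and a table: "In addition, the pairwise LSMeans differences between the doses will be tabulated".

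The five C21 doses ascend in one order in every subject, and Section 9.9 states "Randomisation will not be used". Section 11.2.1 describes a safeguard against changes during the session: "The non-infused arm is used as a contemporaneous control to account for any minor changes in FBF affecting both arms". Nothing in Section 17.5 uses that arm.

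**The concern.** The model compares absolute flow at one dose with absolute flow at another, measured later in the same session. If resting flow moves during the session, for example with temperature or arousal, the movement enters the LSMeans and the pairwise differences one for one. Nothing in the model can tell it from a drug effect.

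The model also has no reference level. If C21 raised flow equally at all five doses, the pairwise differences would correctly be about zero, but the LSMeans would be absolute flows with nothing to show that flow had risen. The Section 17.5.1 table would show it, but no interval is planned there. One could be worked out by hand for n = 5 as mean ± 1.24 SD.

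So a rising curve could be drift, and a flat one could be a drug active at every dose. Section 6.5 says the data are to guide later studies of AT2 receptor agonists, so the curve should be readable on its own.

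**Working it through.** The plan states no SD, drift, alpha or power, so there is no figure of its own to reproduce.

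**Step 1: aliasing (needs no assumption).** Inputs are 5 subjects (Section 9.3) and 5 doses in fixed order (Section 10.5). The planned design has 5 subject columns and 4 dose contrasts, rank 9. Adding a linear period column leaves the rank at 9, so period is completely aliased with dose. The sequence lasts at least 5 × 5 + 4 × 15 = 85 min from the start of the first infusion to the end of the last.

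**Step 2: bias.** With no drug effect and resting flow rising by a fraction d per dose step, 200 versus 3 μg/min is four steps apart, so the apparent effect is (1 + d)^4 − 1:
- d = 1%: 1.01^4 − 1 = 4.1%
- d = 2%: 1.02^4 − 1 = 8.2%
- d = 5%: 1.05^4 − 1 = 21.6%

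**Step 3: how often it would look real.** Assumed: 8 recordings per occasion (Section 11.2.1 gives about 8 per infusion), recording CV 15%, occasion SD 10%, response SD 5% per subject and dose, noise on the log scale. In balanced data the planned model is a two-way subject + dose analysis with 16 residual df. In 20,000 simulated trials per setting, a two-sided 5% test of 200 versus 3 with no drug effect rejected as follows:

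| Drift per step | ln(max), occasion SD 5% | 10% | 15% | ln(mean/baseline mean) |
|---|---|---|---|---|
| 1% | 7.9% | 6.9% | 6.4% | about 5% |
| 2% | 17.3% | 12.9% | 10.2% | about 5% |
| 5% | 71.0% | 52.1% | 36.1% | about 5% |

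The last column ran from 4.7% to 5.2%. It assumes that each baseline shares the drift of the infusion that follows it. With recording noise normal on the raw scale instead, the middle column becomes about 7%, 15% and 58%.

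**Step 4: a common effect.** If the true effect is +50% at every dose, the pairwise differences are about 0. The LSMeans of the log ratio recover +50%, with a 95% CI factor of about ×/÷ 1.09, 1.13 or 1.17 when occasion variation is fully, half or not shared between baseline and infusion.

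**Step 5: precision.** Take a true 30% difference (200 versus 3), so ln 1.3 = 0.262, with SE = residual SD × √(2/5) and power from the noncentral t on 16 df.
- ln(mean), no baseline: SD = √(0.10² + 0.05² + 0.15²/8) = 0.124; SE 0.078; power 88%.
- ln(mean/baseline mean), fully shared: SD = √(0.05² + 2 × 0.15²/8) = 0.090; SE 0.057; power 99%.
- Half shared (add 0.10² to the variance): SD 0.135; SE 0.085; power 82%.
- Not shared (add 2 × 0.10²): SD 0.168; SE 0.106; power 64%.
- ln(max), no baseline, by simulation: 77% (82% with raw-scale noise).

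**Step 6: maximum or mean.** With no drug effect, the maximum of 8 recordings over a baseline mean reads +14.8%, +22.4% or +30.3% at recording CV 10%, 15% or 20%. The number of baseline recordings is not stated. If it were 4, maximum over maximum would read +4.0%, +6.0% or +8.1%, and mean over mean at most +0.2%.

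**Step 7: carry-over into the next baseline.** If 10% or 25% of the previous log effect persists, a true +50% at every dose reads 1.5^0.90 − 1 = 44% or 1.5^0.75 − 1 = 36% from the second dose on. With true effects of 0, 5, 10, 20 and 30%, 25% carry-over makes the last dose read 1.30/1.20^0.25 − 1 = 24%, where the model without baseline would read 30%.

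**The case against.** The strongest reply is that the plan already has a baseline-referenced dose-response display: the Section 17.5.1 table gives percent change by dose across all five doses. The fault is then confined to one secondary display in an open-label study of five subjects with no sample-size basis. This stands as a limit on scope. It does not repair Section 17.5.2, which is the only model and the only analysis named for the dose-response endpoint.

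The pairwise table carries no alpha or decision rule, so the rejection rates describe a test the protocol does not state. They also rest on assumed drift, and at 1% per step the excess over 5% is small. The protocol reduces drift with rest, a quiet temperate room and wash-outs. These points stand on size. The bias in Step 2 needs no test, and the protocol itself expects changes affecting both arms.

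The remedy has costs. The ratio carries baseline noise and is biased down by carry-over, so it can lose precision and exchanges one possible bias for another. This stands and is quantified in Steps 5 and 7. Changing from maximum to mean is not needed to remove drift from the contrasts: maximum over maximum with equal numbers of recordings also holds about 5%. The mean matters for the level of each LSMean when the numbers differ.

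Finally, Section 17 defers detail to a separate SAP. That SAP is to elaborate the principal features stated here, and the dependent variable is one of them. It could still correct the point.

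**Conclusion.** The concern holds and should be fixed. As written, the Section 17.5.2 curve and its pairwise differences confound dose with time in session, and the model ignores the recorded data that could help separate them. This follows from the design and needs no assumption.

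Its practical size does need assumptions: +4% to +22% for 200 versus 3 μg/min at 1% to 5% drift per step, and 6% to 71% nominal rejection over occasion SDs of 5% to 15%. The case rests on validity. Power can move either way, to between 64% and 99% for the ratio, against 77% for the planned response.

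Two limits remain after the fix. Drift between a baseline and its own infusion, and altered responsiveness on repeated dosing, stay confounded with order. The primary summary in Section 17.5.1 is not at fault.

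**What to change.** In Section 17.5.2, the synopsis and the SAP:

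- Make the response ln(FBF during infusion / FBF at that dose's own pre-dose baseline), using the mean of the recordings for both, never a maximum over a mean.
- Keep dose as class effect, subject as random and Kenward-Roger.
- Report each dose's LSMean with a 95% CI, back-transformed to percent change, beside the Section 17.5.1 table. Keep the pairwise table.
- Plot the five pre-dose baselines in order, so that residual drug effect or drift can be seen.
- Show the non-infused arm at the same time points as a check on shared drift.
- State as a limitation that order remains confounded with within-cycle drift and altered responsiveness.

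Section 11.2.1 should also state how many recordings make up each baseline.

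The cost is wording: the baseline and both-arm measurements are already planned, and no visit, subject or change to dosing is needed. The statistical price is baseline noise (64% power against 88% for ln(mean) without baseline if occasion variation is not shared) and downward bias if drug effect persists into the next baseline. The SAP is to be signed before database lock, so the change should be made by then.
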